- The study design would implement a randomized non-blinded clinical trial. Randomization will be performed by having sealed envelopes at the time of enrollment with either "original" or "VSP" written on cards.
- Both groups of patients will be treated by a team of oral and maxillofacial surgery residents and attending surgeons.
- The patients will be divided into two groups, the treatment group and control group. Records for both groups will be evaluated by the investigators and the patients will be asked to follow up in the OMFS Clinic at Memorial Hermann and treated by the Oral & Maxillofacial Surgery service.
 - The treatment group corresponds to patients undergoing mandibular reconstruction via open reduction internal fixation (intraoral or extraoral approach) utilizing virtual surgical planning via 3D Systems, bite registration and fabrication of occlusal splint via intraoral digital scanner, and mandibular hardware
 - The control group will include patients that undergo mandibular reconstruction via open reduction internal fixation (intraoral or extraoral approach) in standard fashion (without virtual surgical planning assistance and occlusal splint)

Study Population

Our study population consists of all patients with complex mandible fractures presenting to the University of Texas Health Science Center at Houston, Department of Oral & Maxillofacial Surgery facility at Memorial Hermann Hospital between October 2019 and October 2021 (until adequate data is obtained for significant statistical analysis).

- We anticipate recruitment of approximately 50 patients (25 patients for each control and treatment group) from Memorial Hermann Hospital. The control group will undergo mandibular fixation via standard open reduction internal fixation techniques. The VSP group will undergo mandibular fixation with standard open reduction internal fixation techniques and utilization of intraoperative occlusal splint, Virtual Surgical Planning via 3D Systems, and Stryker Anatomical Models.
- Inclusion criteria:
 - Patient consent
 - Male or female; 18 years or older
 - Complex mandible fracture (at least two fractures) that require ORIF of at least one fracture.
- Exclusion criteria:
 - Patient refusal to participate in study
 - Infected mandible fracture
 - Closed reduction treatment of mandible fracture
 - Fractures older than 2-3 weeks at the time of treatment
 -

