- The research team will periodically review its protocols to ensure maximal patient safety and data validity.

Statistics

- Generalized linear model will be used to identify data distribution differences between the two study groups.
- This data will be recorded using a standardized data sheet to be shared within the department.
- Power analysis was performed for an f-test, and to show a large effect size ($f=0.4$) between the groups will require:
 - $n = 25$ patients/group to achieve a power of 0.8 and a significant level of 0.05.
- **ANOVA-based power analysis figures require:**
 - $n = 26$ patients/group for a large effect size
 - $n = 64$ patients/group for a medium effect size
 - $n = 393$ patients/group for a small effect size

Ethics

- A written informed consent will be obtained from the adult subject. This site has submitted the consent documents for CPHS review.
- IRB approval will be sought from CPHS (Committee for the Protection of Human Subjects).
- Treatment and clinical management will not be affected by this study. The surgical procedure investigated in this study is considered standard of care.
- Informed consent for the review of records and permission to conduct additional questionnaires and measurements at each follow up appointment will be obtained from each patient prior to commencing the study.
- To protect the privacy of subjects, only members of the research staff including the attending doctors, residents, will have access to patient health information

Data Handling & Record Keeping

- Data collected electronically through the medical record system and recorded on the data sheets attached to this protocol. Access to source documents will be per respective EHR guidelines on computers that are encrypted, and password protected. The data sheets, including consents, will be kept with the principal investigator in a locked cabinet. The patients will also receive a copy of their consent forms. HIPAA compliance guidelines will always be used.
- Human subjects will not be directly identifiable, but only identifiable in the study database through identifying information (Hospital MRN)
- Age of patient will be recorded to replace birth date. Only specific disease information, sex, and age as potential identifier will be used. No identifiable patient name, number or birth date will be used in this study and subsequent publications.

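### The Statistics section gives both 25 and 26 patients per group for what is in effect one two-group F-test at f = 0.4; the planned 25 gives 79.1% power, just under the stated 0.8

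*Combined protocol and SAP*

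**What the plan says.** The Statistics section of the combined protocol and SAP contains two sample-size statements, one after the other.

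- The first is introduced by "Power analysis was performed for an f-test, and to show a large effect size ($f=0.4$) between the groups will require" and gives "n = 25$ patients/group to achieve a power of 0.8 and a significant level of 0.05".
- The second sits under "ANOVA-based power analysis figures require". Its first line reads "n = 26$ patients/group for a large effect size", followed by 64 per group for a medium effect and 393 for a small one. It does not restate f, alpha or power.

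The same section describes the analysis as a two-group comparison: "Generalized linear model will be used to identify data distribution differences between the two study groups". General Information and Study Design describe two groups, with an even split. Study Population uses the lower of the two figures: "We anticipate recruitment of approximately 50 patients (25 patients for each control and treatment group").

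**The concern.** With two groups, an F-test for a difference in means and a one-way ANOVA are the same test. If both statements refer to f = 0.4, alpha 0.05 and power 0.8, they should give the same number, and they do not. Nothing in the documents says why, or which line governs.

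What is at stake is how the sample-size basis is stated. The recruitment figure matches the 25, while the adjacent list puts the requirement one patient per group higher. Anyone who checks the stated F-test at 25 per group will get slightly less than the stated power, and a trial report would have two figures to choose from.

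**Working it through.** **Inputs**

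- Two groups, equal allocation (General Information; Study Design).
- F-test with f = 0.4, alpha 0.05, power 0.8 (Statistics, first statement). For two equal groups d = 2f, so f = 0.4 is a difference of 0.8 SD.
- 25 per group (Statistics, first statement; Study Population).
- 26, 64 and 393 per group for large, medium and small effects (Statistics, ANOVA-based list).
- Assumption: medium and small mean f = 0.25 and f = 0.1. The documents define only the large effect, as 0.4.

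**Step 1: where the 25 could come from.** The normal approximation for two means is

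n per group = 2 × (z for two-sided alpha + z for power)² / d² = 2 × (1.960 + 0.842)² / 0.8² = 24.53, which rounds up to 25.

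This reproduces the 25, but the documents do not say that it was the method used. Applied to all three effect sizes and rounded up, it gives 25, 63 and 393, so it does not produce the printed 26 or 64.

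**Step 2: where the 26, 64 and 393 come from.** The exact power of the two-group F-test uses the noncentral F distribution with df1 = 1, df2 = 2n − 2 and noncentrality λ = f² × 2n. Solving for 80% power at alpha 0.05:

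| Effect | f | Exact n per group | Nearest integer | Printed |
|---|---|---|---|---|
| Large | 0.4 | 25.52 | 26 | 26 |
| Medium | 0.25 | 63.77 | 64 | 64 |
| Small | 0.1 | 393.41 | 393 | 393 |

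All three printed figures match. This supports reading the list as the same test, alpha and power as the first statement.

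**Step 3: power at 25 and 26, f = 0.4.**

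- n = 25: λ = 0.16 × 50 = 8.00, df2 = 48, power 0.7915.
- n = 26: λ = 0.16 × 52 = 8.32, df2 = 50, power 0.8075.

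A two-sided t-test at d = 0.8 gives the same values. The shortfall at 25 is 0.8000 − 0.7915 = 0.0085, or 0.85 percentage points.

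**Step 4: effect detectable with exactly 80% power.**

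- n = 25: f = 0.404 (d = 0.81).
- n = 26: f = 0.396 (d = 0.79).

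**Step 5: other readings of the 25.** At f = 0.4, three groups would need 22 per group and four groups 19. A one-sided test would need 20 (normal approximation) or 21 (exact t-test). Allowing for one to three covariates through the degrees of freedom alone leaves power at 25 per group between 79.0% and 79.1%. None of these makes 25 the required number.

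**The case against.** The strongest case on the other side is that neither figure is really wrong. The normal approximation gives 25 and the exact test gives 26, so what is missing is the name of the method. At the single decimal the protocol prints, 79.1% is 0.8. Recruitment is only approximate, and its end date is left open, so 52 patients would already fit the plan. Study Population does not cite the power calculation, so the link to the 25 is inferred from the matching number. The ANOVA list does not state its inputs. And 393 also falls short by the exact test (79.96%; strict rounding up gives 394), so it may seem inconsistent to query the 25 and leave the 393.

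Much of this stands, and it keeps the point small. The consequence for the trial is negligible, and both the reading of the list and the link to Study Population are inferences, though well supported. It does not remove the conflict. The plan calls the 25 an F-test result, and its own next lines give 26 for what works out to be that test. The 393 is a different case: it agrees with the rest of its list under nearest-integer rounding and is short by 0.04 points, against 0.85 for the 25. Rounded in the same way, 25.52 becomes 26, not 25.

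**Conclusion.** The concern holds as a minor discrepancy. The section gives two sample sizes for what is in effect one calculation, and the one adopted for recruitment gives 79.1% power by the exact F-test, not 80%. The gap is 0.85 percentage points, or one patient per group, and it moves the detectable effect from f = 0.400 to f = 0.404.

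This rests on two equal groups, the usual normal, equal-variance F-test, alpha 0.05 in that test (equivalent to a two-sided t-test), and the inference that the ANOVA-based list uses f = 0.4 and 80% power for its large effect. The powers also count all 25 or 26 patients per group as analysed; the documents give no dropout allowance. The finding concerns how the figure is stated. It does not question whether the trial is adequate at f = 0.4.

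**What to change.** Replace the two large-effect lines in Statistics with a single statement that names the method, for example: *25 patients per group give 79% power (exact two-group F-test, two-sided alpha 0.05) for f = 0.4, a difference of 0.8 SD, if all are analysed; 26 per group would give 80.7%.* The 64 and 393 can stay, preferably with a note that the list is rounded to the nearest integer.

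This costs one sentence and a stated power of 79% instead of 80%. If the sponsor prefers to keep the 0.8 target, stating 26 per group (52 in total) in both Statistics and Study Population also removes the conflict, at a cost of two more patients: 52 − 50 = 2.

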**Comparison of Operating Room Time Length with the Use of Virtual Surgical Planning Versus
Conventional Treatment of Mandible Fractures**

NCT04283981

Version Date: 02/10/2021

Protocol Title:	Comparison of Operating Room Time Length with the Use of Virtual Surgical Planning Versus Conventional Treatment of Mandible Fractures
Principal Investigator:	[name] [name]
UTHealth Co-Investigators:	[name] DDS MD FACS; [name] DDS MD PhD FACS; [name] DDS; [name] MD; [name] DDS; [name] DDS
Study Coordinators:	[name]; [name] APRN FNP; [name]
Population:	All patients presenting with diagnosed mandible fracture at Memorial Hermann Hospital
Number of Sites:	Memorial Hermann Hospital
Study Duration:	Between November 2019 and November 2021 (until adequate data is obtained for significant statistical analysis)
Subject Duration:	From the initial preoperative evaluation to end of treatment which is 2 months

General Information

Patients at Memorial Hermann Hospital who have an isolated mandibular fracture and who are appropriately consented will partake in this study. They will be split evenly into 2 groups which are virtual surgical planning (VSP) and the conventional surgery. The conventional surgery involves having medical grade CT in order to assess the mandible fracture and having an open reduction and internal fixation of the fracture. The reconstruction plate will be bent intra-operatively. VSP patients will also receive the medical grade CT and also receive intraoral scans for aid in assessing occlusion. 3D models of the patient's jaws will be made and set into the proper occlusion. A reconstruction plate will be bent before the surgery using these models to be used at the time of surgery. Advancements in VSP technology increasingly demonstrate improvements in operative efficiency and reduce operating time. Pre-surgical planning and fabricated guides can potentially improve intraoperative efficiency, postoperative outcomes, and minimize complications. Additionally, use of this technology may permit a reduction of operating costs associated with longer operating room and anesthesia times in conventional treatments. Another challenge presented with VSP is turn over time from the actual planning and fabrication of splints or anatomical models to having them ready for surgery. This can take between one to two weeks and delay treatment for acute trauma cases.

Objectives

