 - Other etiologies than trauma of the mandibular fracture or pathologic fracture secondary to benign or malignant pathology that may require resection
 - Pregnant patients will NOT be excluded from the study
 - Co-morbidities (auto-immune disease, osteoporosis, titanium or metal allergy, uncontrolled diabetes (A1c greater than 8)

Patient would be enrolled upon evaluation and consent for mandibular reconstruction at the University of Texas Health Science Center at Houston, Department of Oral & Maxillofacial Surgery treatment facility at Memorial Hermann Hospital - Texas Medical Center

Study Procedures

- No additional time will be required from participants than the time required for the normal care, treatments, or management. Patients will not be charged anything additional to participate in the study and will also not receive any compensation.
- Patients will have post-operative CT scan to ensure adequate reduction and fixation of fractures
- Patients will be re-evaluated at 3 follow up visits within 6 weeks to determine mandible fracture healing.
 - Post-op (prior to discharge), 1 week, 3 weeks +/- 1 week, 6 weeks +/- 1 week
- Collected data will include:
 - Age, gender, operating time (ORIF time, total operating time), fracture pattern
 - ORIF time will be defined as starting after the dissection is complete and fractures are reduced until final screws are placed.
 - Ideally the dissection, reduction, closure should not change from the control to the treatment
 - Accuracy of fracture reduction
 - Type of archbars, fit of guides, type of approach
 - Surgical revisions, infections, mouth opening
 - Hardware failure defined as plate fracture or screw loosening
- Once data is collected, variability will be calculated within individual test results.

Data & Safety Monitoring

- Adverse events
 - Expected adverse events: pain, infection, bleeding, swelling, trismus, possible nerve damage, damage to adjacent structures
 - Unexpected adverse events: repeat fractures, trauma post-surgery, plate fractures, loose screws, mal-unions, non-unions, poor cosmetic outcome, delayed healing
 - Potential serious adverse events: sepsis from infection, osteomyelitis
- Unanticipated problems will be discussed amongst investigators.
- Methods of measuring results will be discussed amongst investigators and standardized so that measurements remain consistent from investigator to investigator.

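### Ethics says management is unaffected, yet a random envelope decides VSP use and possibly time to surgery, and the data list contains nothing that would show it

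*Combined protocol and SAP*

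**What the plan says.** The Ethics section of the combined protocol and SAP states: "Treatment and clinical management will not be affected by this study". It adds: "The surgical procedure investigated in this study is considered standard of care".

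Other sections describe an intervention assigned by chance. Study Design says: "Randomization will be performed by having sealed envelopes at the time of enrollment". General Information, Study Design and Study Population give the VSP arm an intraoral scan, anatomical models, an occlusal splint and a plate bent before the operation; the control arm has conventional fixation without them. On the turn-over of VSP planning and fabrication, General Information says: "This can take between one to two weeks and delay treatment for acute trauma cases". Objectives and Background Information make it a study question whether remote printing can shorten that turn-over. Neither gives an achieved or a maximum time.

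On consent, Ethics opens with a general promise: "A written informed consent will be obtained from the adult subject". The only content it then describes is: "Informed consent for the review of records and permission to conduct additional questionnaires and measurements at each follow up appointment". Study Design describes much the same scope, adding follow-up attendance and a formal examination. Study Population says: "Patient would be enrolled upon evaluation and consent for mandibular reconstruction".

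The exclusion criteria in Study Population include: "Fractures older than 2-3 weeks at the time of treatment".

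**The concern.** If the envelope decides which pre-operative work-up and devices a patient receives, and may change when the operation happens, the study does affect management. The Ethics sentence then contradicts the rest of the protocol on a matter that an ethics committee relies on.

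Two statistical consequences follow. First, the trial asks whether VSP turn-over can be shortened, but the listed data include nothing from which turn-over or time to surgery could be derived. A saving in theatre minutes could not be set against any added wait. Second, an eligibility rule judged at treatment is judged after allocation. If only one arm has a planning wait, that rule can remove patients from that arm alone, and the groups compared are then no longer the groups randomised.

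**Working it through.** The plan gives no figure for delay by arm, and its sample-size figures do not bear on this point. The check is mainly a comparison of sections, followed by one piece of arithmetic.

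**1. Does allocation affect management?** Study Design has the envelope choose the arm. The arm determines the scan, models, splint and pre-bent plate. Management therefore differs by allocation even if no patient waits a day longer. Calling the procedure standard of care does not remove the conflict: choosing between two accepted pathways by chance still changes what the individual patient receives.

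**2. What does the described consent cover?** Ethics and Study Design cover records, questionnaires, measurements and follow-up. Study Population refers to consent for the operation. No section describes consent to random assignment or to a possible change in time to surgery.

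**3. What can the listed data show?** The Study Procedures list contains age, gender, ORIF time, total operating time, fracture pattern, accuracy of reduction, archbar type, guide fit, approach, revisions, infections, mouth opening and hardware failure. The quantities needed are:
- turn-over time = date VSP materials ready − date of allocation (taken here as the start of planning);
- time from injury to surgery = surgery date − injury date;
- time from allocation to surgery = surgery date − allocation date.

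None of these dates is listed, so none of the three can be derived from the list.

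**4. How does the turn-over sit against the fracture-age limit?** Inputs: turn-over T = 7 or 14 days (General Information); limit L = 14 or 21 days (Study Population, which gives a range and not one cut-off). Assume that planning starts at allocation and surgery waits for the materials. The oldest fracture at allocation that could still be treated within the limit is L − T.

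| Limit L (days) | Turn-over T (days) | L − T (days) |
|---|---|---|
| 14 | 7 | 7 |
| 14 | 14 | 0 |
| 21 | 7 | 14 |
| 21 | 14 | 7 |

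The control arm has no planning wait. With 25 patients planned per group, each patient removed from the VSP arm is 1/25 = 4% of it. How many would be removed is unknown, because fracture age at enrolment is not given.

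**5. Can the extra delay be computed?** No. Let w be the usual wait from allocation to surgery in the control arm, which the documents do not state. If planning runs alongside that wait, the extra delay is max(0, T − w). For T = 7 this runs from 7 days (w = 0) to 0 (w ≥ 7). For T = 14 it runs from 14 days (w = 0) to 0 (w ≥ 14). The documents therefore allow anything from 0 to 14 days, and a shorter T from remote printing would lower the upper end.

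**The case against.** The strongest reply is that little is hidden. The protocol states the possible delay in General Information and the randomisation in Study Design, promises written consent, and says that the consent documents went to the ethics committee. The turn-over figure is a general remark about VSP, and the study hopes to shorten it. Data sheets are said to be attached and may hold dates. The fracture-age rule cannot be applied without knowing fracture age. The ORIF-time definition is unaffected.

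Much of this stands, and it rules out several stronger readings that a reader might infer:
- *That every VSP patient will wait one to two weeks.* The text says that it can take that long; the turn-over expected in this trial is not stated.
- *That participants or the committee are told nothing will change.* The consent form cannot be seen here, so its content cannot be judged.
- *That longer waiting will raise infections.* No section states such a link; infection appears only as an exclusion, an outcome and an adverse event.
- *That the delay uses up 33% (7/21) to 100% (14/14) of the permitted fracture age.* These ratios pair the extremes of two ranges and ignore the control arm's wait, so they do not measure what allocation adds.
- *That nothing will be recorded.* The attached data sheets are not available; only the protocol's list can be assessed.

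What the reply does not do is reconcile the Ethics sentence with random assignment, or supply a listed variable that answers the turn-over question.

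**Conclusion.** The contradiction is in the text and should be corrected. The Ethics statement cannot hold beside the envelope allocation in Study Design and the possible delay in General Information. The protocol's description of consent does not mention random assignment or timing. As listed, the data cannot answer the turn-over aim or show whether allocation changed time to surgery.

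The extra delay cannot be sized from the documents. The only figures available are conditional: if surgery waits 7 to 14 days from allocation, VSP patients whose fractures are older than 0 to 14 days at allocation, depending on the pairing, would pass the limit before treatment. One-sided loss after randomisation is therefore a possibility, not a forecast. The primary comparison of ORIF time is not invalidated by the wording conflict; it would be at risk only if such losses occurred and went unreported. No view is taken on what delay is acceptable.

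**What to change.** - Reconcile General Information, Study Design, Study Population, Study Procedures and Ethics on whether allocation affects management and timing. Include the Study Procedures statement that participants give no time beyond normal care, if it is meant to cover waiting.
- Align the protocol's consent description with the reconciled text.
- Add four dates to the Study Procedures data list: injury, allocation, VSP materials ready (VSP arm only) and surgery.
- Report VSP turn-over time, and by arm the time from injury to surgery, the time from allocation to surgery, and the number excluded for fracture age after allocation.

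The cost is an amendment to protocol and consent wording, with ethics committee review, and a few dates per patient. For about 50 patients that is 25 × 4 + 25 × 3 = 175 date entries. The allocation date should be noted when the envelope is opened, because nothing in the protocol says that it otherwise enters the medical record. The sample size and the primary endpoint do not change.
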